1.2 SCHEMATIC OF STUDY DESIGN

An overview of the study design is provided in [Figure 1](#).

Figure 1 Overview of Study Design: Parts A and B

1.3 SCHEDULE OF ACTIVITIES

The schedule of the activities is provided in [Table 1](#) and details in [Table 2](#).

Table 1 Schedule of Activities Treatment Period, 21-day Cycles, Q3W

	Screening	Treatment period, 21-day cycles, Q3W dosing																					Post-Treatment					
Cycle	Screening/ Baseline ^a	Cycle 1			Cycle 2			Cycle 3			Cycle 4			Cycle 5			Cycle 6			Subsequent Cycles to 24 Months	End of Treatment (EoT) Early Discontinuation ^g	Safety Follow-up/End of Study (EoS)	Survival Follow up ^s	Unscheduled Safety (for IRR refer to Table 2) ^h				
Study visit window			± 1 d	± 2d	+ 2d		± 2d	± 2d		± 1d	± 2d	± 2d		± 2d	± 2d	± 2d	± 2d	± 2d	± 2d	± 2d	± 2d	28 (± 7) days after last dose	90 (± 7) days after last dose	90 (± 7) days after Safety FU visit and then every 3 months (± 14 days)				
Day	D-28 to D-1 ^m	Day 1 ^c	Day 2	Day 4	Day 8	Day 15	Day 1 ^c	Day 2	Day 8	Day 1 ^c	Day 2	Day 4	Day 8	Day 15	Day 1 ^c	Day 2	Day 8	Day 15	Day 1 ^c	Day 8 ^h	Day 1 ^c	Day 8 ^h	Day 1 ^c	Day 8 ^h				
Study Week		1		2	3	4		5	7			8	9	10		11	12	13	14	16	17	≥ 19						
ASSESSMENTS^c																												
Informed Consent ^b	X																											
Eligibility criteria	X																											
Demography	X																											
Medical/Cancer History	X																											
Complete physical exam ^d	X																											
Complete neurological exam ^o	X																											
Royal Marsden Risk Score	X																											
Chest X-ray ^p	X																										(x)	
Brain CT MRI ⁱ	X																										(x)	
Echocardiography (TTE/MUGA)	X																											
Height	X																											
Weight ^c	X	X					X			X					X				X		X		X		X		(x)	
ECOG	X	X					X			X					X				X		X		X		X		(x)	
Vital Signs ^q	X	X	X	X	X	X	X	X	X	X	X	X	X	X	X	X	X	X	X	(x)	X	(x)	X	(x)	X	(x)	(x)	
Targeted physical/neurological exam ⁱ		X	X	X	X	X	X	X	X	X	X	X	X	X	X	X	X	X	X	(x)	X	(x)	X	(x)	X	(x)	(x)	
Triplicate 12-lead ECG ⁱ	X	pre-dose					pre-dose			pre-dose										pre-dose								(x)
Adverse Events ^k		x (continuously monitored)																										
Previous and Concomitant Treatments		x (continuously monitored)																										
STUDY DRUG ADMINISTRATION																												
Premedication ^u		X					X			X					X				X		X		X		X			
Administration of RO7296682		X					X			X					X				X		X		X		X			
TUMOR ASSESSMENT																												
CT/MRI scan ^o	X													X										X	X ^q	X ^q	X	

Table 1 Schedule of Activities Treatment Period, 21-day Cycles, Q3W (cont.)

Cycle	Screening	Treatment period, 21-day cycles, Q3W dosing																								Post-Treatment																
	Screening/ Baseline ^a	Cycle 1						Cycle 2						Cycle 3						Cycle 4						Cycle 5						Cycle 6						Subsequent Cycles to 24 Months		End of Treatment (EoT)/ Early Discontinuation ^f	Safety Follow up/End of Study (EoS) ^g	Survival Follow up ^h
Study visit window				± 1 d	± 2d	+ 2d		± 2d	± 2d		± 1d	± 2d		± 2d	± 2d		± 2d	± 2d		± 2d	± 2d		± 2d	± 2d		± 2d	± 2d		± 2d	± 2d	28 (± 7) days after last dose	90 (± 7) days after last dose	90 (± 7) days after Safety FU visit and then every 3 months (± 14 days)									
Day	D 28 to D 1 ^m	Day 1 ^c	Day 2	Day 4	Day 8	Day 15	Day 1 ^c	Day 2	Day 8	Day 1 ^c	Day 2	Day 4	Day 8	Day 15	Day 1 ^c	Day 2	Day 8	Day 15	Day 1 ^c	Day 8 ^h	Day 1 ^c	Day 8 ^h	Day 1 ^c	Day 8 ^h	Day 1 ^c	Day 8 ^h	Day 1 ^c	Day 8 ^h														
Study Week		1		2	3		4		5		6		7		8		9		10		11		12		13		14		15		16		17	≥ 19								
LOCAL LABORATORY ASSESSMENTS^c																																										
Lipids ^l	x																																									
Viral serology (HBV, HCV, HIV) ^l	x																																									
Auto antibody Panel ^{n 1}	x						x			x																											(x)					
TSH, free T3 (or total T3), free T4 ^l	x	x					x			x																											(x)					
Hematology ^l	x	x	x	x	x	x	x	x	x	x	x	x	x	x	x	x	x	x	x	(x)	x	(x)	x	(x)	x	(x)	x	(x)	x	(x)	x	x	x	x	(x)							
Clinical Chemistry ^l	x	x	x	x	x	x	x	x	x	x	x	x	x	x	x	x	x	x	x	(x)	x	(x)	x	(x)	x	(x)	x	(x)	x	(x)	x	x	x	(x)								
Coagulation ^l	x	x			x	x	x			x																										(x)						
Urinalysis ^l	x	x			x	x			x	x																										(x)						
Pregnancy Test ^m	x	Urine or serum pregnancy test performed prior to each treatment, with result available prior to dosing																								x	x															
IgE/Tryptase		Collected centrally and locally. Please refer to Table 2																																								
CENTRAL LABORATORY ASSESSMENTS																																										
PK RO7296682																																										
ADA RO7296682																																										
Receptor Occupancy																																										
Blood FACS																																										
PD Cytokines																																										
█																																										
Soluble tumor and inflammatory markers																																										
RBR (DNA and RNA)																																										
Blood GEP																																										
█																																										
IgE/Tryptase																																										
BIOPSIES																																										
Archival biopsy																																										
Tumor biopsy																																										
Skin Biopsy																																										
Optional biopsy																																										
MICROBIOME (optional, Part B ONLY)																																										
Stool samples ^l	x																																			(x)						
Post Study																																										
New anti cancer treatment																																					x					
Survival follow up phone call																																					x					

Table 1 Schedule of Activities Treatment Period, 21-day Cycles, Q3W (cont.)

a)	The screening period starts with the signing of the Informed Consent Form. Results of standard-of-care tests, tumor assessments or examinations performed prior to obtaining informed consent and within the defined window may be used as screening and baseline assessments; such tests do not need to be repeated for screening purposes.
b)	Informed consent must be obtained before any study-specific procedures are conducted. (Note: Two separate consents are embedded within the main Informed Consent Form. In addition, the study contains a separate Informed Consent Form for optional stool samples, in Part B only.)
c)	On treatment days, all assessments should be performed before dose is administered, unless otherwise specified. If body weight and local lab assessments (except for pregnancy test, which must be done on the treatment day with results available prior to dosing) are performed \leq 3 days before the day of the planned dosing, these values can be used and recorded in the electronic case report form (eCRF).
d)	Complete physical exam should include an evaluation of the head and neck, eyes, ears, nose, and throat, and the cardiovascular, dermatological, musculoskeletal, respiratory, gastrointestinal, genitourinary, and neurological systems. Any abnormality identified at baseline should be recorded on the General Medical History and Baseline Conditions eCRF.
e)	Complete neurological exam: Neurologic examinations should include an assessment of mental status, cranial nerves, muscle strength, sensation, and coordination. Results of the neurological exam should be documented in the participant's chart. Mental status checks do not require completion of a validated mental status questionnaire.
f)	Stool samples (optional): Only collected in Part B, dose expansion and provided participant signed the consent for optional stool samples. For details on when samples should be collected, refer to Section 8.9.
g)	Vital signs: please refer to the hourly Table 2 for details.
h)	Optional safety visits Optional safety visits upon discretion of the Investigator.
i)	Targeted physical/neurological examinations: Examinations should be limited to systems of primary relevance (i.e., cardiovascular, respiratory, neurologic, and any system that might be associated with tumor assessment [e.g., lymph nodes, liver, and spleen and those systems associated with symptoms], or potential drug-related toxicity).
j)	Triplicate 12-lead electrocardiograms (ECGs): Three individual ECG tracings should be obtained as closely as possible in succession, but no more than 5 minutes apart. The average of the 3 readings will be used to determine ECG intervals (e.g., PR, QRS, and QT). Additional unscheduled ECG assessments should be performed in case of abnormalities and if clinical symptoms occur. Recordings should be performed prior to blood draws and prior to dosing RO7296682.
k)	Adverse Events: Prior first study drug administration only SAEs caused by a protocol-mandated intervention should be reported. After initiation of study drug all adverse events will be reported as outlined in protocol Section 8.3.1 and Section 8.3.2. Note: All AEs and laboratory safety measurements will be graded per current NCI CTCAE 5.0.
l)	For details on local laboratory assessments please refer to Appendix 4 (Clinical Laboratory Tests).
m)	Perform a serum pregnancy test for women of childbearing potential within 7 days prior to first dose. Thereafter a urine or serum pregnancy test will be performed prior to each treatment dosing with results available before dose is administered. Results must be obtained and reviewed prior to dose administration.
n)	The auto-antibody panel will be assessed at Screening, pre-dose Cycles 2 and 3, and every 6 cycles thereafter. In participants who develop signs and/or symptoms suggestive of auto-immune disease while on-treatment, the auto-antibody panel must be repeated. Participants with confirmed positive serology of at least one of the auto-antibody panel during the course of the study should be discussed between Sponsor and Investigators, and if judged clinically relevant, could be referred to a specialist to exclude an underlying auto-immune disease.

Table 1 Schedule of Activities Treatment Period, 21-day Cycles, Q3W (cont.)

o)	Tumor assessments to be performed according to RECIST 1.1. (Appendix 7). Tumor lesions will be assessed at screening, and every 8 weeks (± 7 days) after first dose (i.e. C1D1) – regardless of any treatment delays – for the first year, and then every 12 weeks (± 7 days) thereafter until disease progression. For participants who discontinue treatment for any other reason than disease progression: a) an end of treatment CT/MRI scan is only to be performed if it was done ≥ 28 days prior to this day, b) CT/MRI scan to be performed at the Safety Follow-Up visit.
p)	Chest X-ray will be performed at baseline, if the baseline tumor assessment does not image the chest/thorax and as clinically indicated during the study treatment period.
q)	End of Treatment (EoT)/ Early Discontinuation Visit: Participants who complete treatment or discontinue early, will be asked to return to the clinic within 28 (+/-7) days after the last dose. The visit at which a response assessment shows progressive disease may be used as the discontinuation visit.
r)	Safety Follow-Up: Participants who complete the study or discontinue from the study early, will be asked to return to the clinic 90 (± 7) days after the last dose treatment with RO7296682. A tumor assessment is to be performed for participants who discontinued the study for reasons other than disease progression.
s)	Survival Follow-Up: The sites will provide to the Sponsor an update on survival status and new anti-cancer treatment 90 (± 7) days after the Safety Follow-Up visit and then every 3 months (± 14 days) thereafter up until 24 months post initial treatment (or until study closure) for each participant enrolled in the study. Contact can be either in person or via a phone call to document.
t)	Baseline brain CT MRI: A CT or MRI scan (with IV contrast unless contraindicated) of the head must be performed at baseline to assess CNS metastasis. In the event of an equivocal CT scan, an MRI scan of the brain is required to confirm or refute the diagnosis of CNS metastases at baseline. If the participant presents CNS metastasis at baseline, on-treatment tumor assessments must also contain a CT or MRI scan of the head. If participant has no brain metastasis at baseline, then CT/MRI scan of the head is only indicated if symptoms suggest potential brain disease.
u)	Pre-medication can be considered prior to the first dose at Investigator discretion. For subsequent infusions, please refer to Section 6.1.2 and Section 8.3.8 . For details in case participants experience IRR, refer to protocol section 8.3.8 .

Table 2 Schedule of Activities Q3W, Details

Cycle	Day	Scheduled Time (h)	Time window ^a	Vital Signs ^h	PK RO729682 ^{b, c, d, e}	ADA RO729682 ^{c, d, e}	Receptor Occupancy	PD blood FACS	PD Cytokines	Archival sample	Tumor Biopsy ^g	Skin Biopsy ^g	Optional Biopsy ^j	Blood GEP	Clinical Genotyping (DNA)	RBR (DNA)	RBR (RNA)	IgE/Tryptase ^f		
Screening/ Baseline	D-28 to D-1			x			x			x	x	x								
Cycle 1	Day 1	Predose		x	x	x	x	x	x				Any visit	x	x	x				
		Half-time of infusion ± 15min		x	x															
		EOI ± 15min		x	x			x	x	x										
	EOI+3 ± 30min		x	x																
	Day 2	24	± 2h	x	x															
	Day 4	72	± 24h	x	x		x	x	x											
	Day 8	168	± 48h	x	x			x	x											
Day 15	336	± 48h	x	x		x	x	x												
Cycle 2	Day 1	Predose		x	x	x	x	x	x					Any visit	x					
		EOI ± 15min		x	x															
		EOI+3 ± 30min		x	x															
Day 2	24	± 2h	x	x																
Day 8	168	± 48h	x	x			x	x		x	x									
Cycle 3	Day 1	Predose		x	x	x	x	x	x						Any visit	x				
		Half-time of infusion ± 15min		x	x															
		EOI ± 15min		x	x			x	x	x										
	EOI+3 ± 30min		x	x																
	Day 2	24	± 2h	x	x															
	Day 4	72	± 24h	x	x		x	x	x											
	Day 8	168	± 48h	x	x			x	x											
Day 15	336	± 48h	x	x		x	x	x												
Cycle 4	Day 1	Predose		x	x	x	x	x	x				Any visit			x				
		EOI ± 15min		x	x															
		EOI+3 ± 30min		x	x															
Day 2	24	± 2h	x	x																
Day 8	168	± 48h	x	x																
Cycle 5	Day 1	Predose		x	x	x	x							Any visit		x				
		EOI ± 15min		x	x															
Subsequent Cycles ^d	Day 1	Predose		x	x	x	x	x only at cycle of tumor assessment	x only at cycle of tumor assessment		x ^g	x ^g								
		EOI ± 15min		x	x															
End of Treatment (EoT) Visit	28 days (± 7) after last dose	At vis t		x	x	x	x													
Safety FU (90d after last dose)		At vis t		x	x	x										x				
In addition, samples to be taken at the following instances:																				
In the event of an IRR ≥ G2 or hypersensitivity event or AE ≥ G3 leading to dose reduction or interruption		At vis t			x	x			x						Any visit					x
		At vis t																		
DLT		At vis t			x	x			x										x	
Unscheduled Visit ⁱ		At vis t			x	x	x	x	x										x	

Table 2 Schedule of Activities Q3W, Details (cont.)

a)	The time windows can be used for flexibility. For example if Day 2 occurs on a Friday, Day 4 can be conducted on the following Monday and Day 8 on the Thursday.
b)	During the course of the study, PK/PD sampling time points may be modified based on emerging data to ensure that PK/PD of RO7296682 can be adequately characterized. In this case, no new additional PK/PD samples will be introduced but sampling times may be modified. Blood for PK/PD should be drawn at the indicated time points.
c)	All blood samples for PK assessments will be collected from an IV line in the opposite arm to the one for drug infusion.
d)	Up to Cycle 5: PK and ADA samples should be taken at indicated time points . Subsequent cycles until 6 months after first dose of RO7296682: PK and ADA samples will be taken on Day 1 of each cycle. Subsequent cycles after first 6 months of RO7296682 treatment: PK and ADA samples will be taken only Day 1 at cycle of tumor assessments .
e)	Unscheduled PK samples will be taken (where feasible) at the time of development of any of the following events, or at the earliest possible convenience thereafter: * DLT * Dose reduction or treatment reduction or interruption due to IRR/CRS event \geq G2 or hypersensitivity event or AE \geq G3. - At time of interruption, collect the unscheduled PK sample and clearly record the reason for this collection (i.e., due to interruption). - At infusion restart and completion, collect scheduled pre, (mid – where applicable) and post infusion time points as noted per SoA.
f)	Tryptase and IgE samples will be collected for local analysis at onset of the reaction. A second sample for central IgE/Tryptase analysis will be collected approximately 48 hours after onset of the reaction.
g)	Fresh tumor biopsy and healthy skin tissue punch biopsy will be taken at baseline (only once all inclusion/exclusion criteria have been met) and at Cycle 2 Day 8. If preliminary data suggest, alternative on-treatment tumor biopsy or healthy skin punch biopsy time points may be considered upon joint agreement between Investigators and the Sponsor. Part A: Mandatory pre- and on-treatment biopsies only done after reaching the Tissue Biomarker Dose. Part B: mandatory pre- and on-treatment biopsies for all participants.
h)	Vital Signs will include measurements of systolic and diastolic blood pressure, respiratory rate, heart rate, and body temperature while the participant is in a sitting or semi-supine position. Vital signs during the infusion are not required to be captured in the eCRF unless abnormalities are observed.
i)	Unscheduled Visits optional samples can be taken at the discretion of the investigator and/or in agreement with the Sponsor.
j)	Optional biopsies: Optional biopsies from pathological and healthy tissue may be taken at the investigator's discretion and with participant's consent at different time points. For example but not limited to Adverse Events , disease progression or long-lasting stable disease in order to characterize the immune resistance mechanisms. For details, see Section 8.8.2.

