To evaluate preliminary anti-tumor activity of RO7296682 according to immune RECIST (iRECIST)	
 • Objective response rate (ORR) • Disease control rate (DCR); defined as ORR + SD rate All according to immune RECIST (iRECIST) 
In addition:
 
 • Duration of response (DoR) • Progression free survival (PFS) • Overall survival (OS) if data are mature
To explore potential effects of ADA	
 • Relationship between ADA status and PK/PD, safety, and efficacy

Objectives	Endpoints
To explore biologic markers that might act as predictors of safety and/or anti-tumor activity of RO7296682	
To explore degree of target binding of RO7296682 (in association with PK) via a receptor occupancy (RO) assay	
 Evaluate RO via ex-vivo assay
To explore the effect of Treg depletion in the skin immune contexture	
 Treatment-induced changes in Treg levels in the skin as compared to baseline.
To explore the effect of Treg depletion on the gut microbiome	
 Treatment-induced changes of the gut microbiome as compared to baseline

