4. STUDY DESIGN

4.1 OVERALL DESIGN

- Study WP41188 is a first-in-human, open-label, multicenter, Phase 1 dose escalation study of single agent RO7296682 in participants with advanced and/or metastatic NSCLC, MEL, HNSCC, OvC, TNBC, or EsC. An overview of the study design is provided in Section 1.2.

All participants will be treated with RO7296682 until disease progression, unacceptable toxicities, withdrawal of consent, or withdrawal of the participant by the Investigator. Participants may continue treatment with RO7296682 for a maximum of 24 months. This period may be adjusted based on the emerging safety and response profile. As with other immunotherapies, treatment beyond progressive disease (i.e. due to pseudo-progression) according to RECIST Version 1.1 can be considered after initial dose, following consultation and agreement between the Sponsor and Investigator.

[figure not shown]
For the maximum number of participants, please refer to Section 9.2.

The study consists of 2 parts: Part A is a single agent dose escalation and Part B is a single agent dose expansion.

- Part A: RO7296682 dose escalation in multiple participant cohorts**

Part A will determine the safety, tolerability, PK/PD profile, and preliminary anti-tumor activity of escalating doses of RO7296682 using a minimum of 3 DLT evaluable participants per cohort (see Section 9.3 for definition of DLT analysis population). The starting dose will be 0.3 mg and the maximum dose is planned to be 500 mg. Participants will receive intravenous (IV) RO7296682 every 3 weeks (Q3W) and the cycle length will be accordingly defined as 21 days. Incremental increases (and potential decreases) between cohorts will be determined by a Bayesian-based continuous reassessment method (CRM) with overdose control measures. Entry into a cohort will be controlled by a 7-day safety window between participants 1 and 2 in each cohort. Please refer to Section 4.1.2.1 for details on the DLT window. At least 3 DLT evaluable participants will be enrolled in each Part A cohort during the dose escalation. For intra-patient dose escalation, please refer to Section 4.1.2.2.

Part A will enroll participants with NSCLC, MEL, OvC, HNSCC, TNBC, or EsC who have progressed on all standard therapies, are intolerant to standard of care (SOC), and/or are non-amenable to SOC, or for whom SOC does not exist.

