In the absence of clinical deterioration any initial assessment of radiological progressive disease should be confirmed by a repeat evaluation at the next time point for tumor

assessment. As with other immunotherapies, treatment beyond RECIST progression could be considered after approval of the Sponsor (see Section 6.7 for details on continuing treatment).

All tumor assessments after baseline may be done within one week of the scheduled visit. Confirmation of objective responses (partial and complete responses) will be done at the next scheduled visit after at least 28 days from the initial response.

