8.11.2 Assessments during Treatment

Under no circumstances will participants who enroll in this study and have completed treatment as specified, be permitted to re-enroll in the study.

All assessments must be performed as per SoA (Section 1.3). Assessments scheduled on the day of study treatment administration should be performed prior to administration of study treatment, unless otherwise noted in the schedule of assessments.

Participants will be treated with study treatment, until disease progression, unacceptable toxicity, withdrawal of consent, or withdraw by Investigator. Participants may receive study treatment for a maximum of 24 months since C1D1.

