3 REFERENCES

Appendix 8

Modified RECIST v1.1 for Immune-based Therapeutics (iRECIST)

Conventional response criteria may not be adequate to characterize the anti-tumor activity of immunotherapeutic agents, which can produce delayed responses that may be preceded by initial apparent radiographic progression, including the appearance of new lesions. Therefore, immunotherapy-specific response criteria adaptations to Response Evaluation Criteria in Solid Tumors, Version 1.1 (RECIST v1.1; [Eisenhauer et al. 2009](#); see list of references at end of this Appendix) have been developed to allow for unconventional response and progression patterns. These include modified RECIST v1.1 for immune-based therapeutics (iRECIST; [Seymour et al. 2017](#)), which was developed by the RECIST working group in an effort to create a common set of criteria that the cancer immunotherapy field could apply to clinical trials.

Response evaluation through use of iRECIST requires collection of tumor assessment data after radiographic progression per RECIST v1.1. Details regarding lesion evaluation are described below. When not otherwise specified, RECIST v1.1 conventions will apply.

Criteria for determining overall response at a single time point per iRECIST are also summarized below. Of note, overall response per iRECIST will not be captured in the electronic Case Report Form (eCRF), but will instead be calculated programmatically by the Sponsor on the basis of investigator-assessed individual lesion data recorded in the eCRF.

iRECIST response status is not a specific component of treatment discontinuation criteria, including decisions about whether to continue treatment beyond progression per RECIST v1.1. Investigators should instead take into account radiologic data and clinical status in making such decisions

EVALUATION OF LESIONS TO SUPPORT iRECIST RESPONSE **ASSESSMENT AFTER DISEASE PROGRESSION PER RECIST V1.1**

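### The Schedule of Activities ends tumor scans at progression while Section 8.1.1 and Appendix 8 call for later ones, so exploratory iRECIST data would depend on site practice

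*Combined protocol and SAP*

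**What the plan says.** The SoA side:

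- Section 1.3, Table 1, footnote o begins "Tumor assessments to be performed according to RECIST 1.1". It sets an 8-week interval for the first year and after that "every 12 weeks (± 7 days) thereafter until disease progression". It does not mention iRECIST or participants who stay on treatment after progression.
- The same footnote limits the end-of-treatment and safety follow-up scans to participants who stop treatment for a reason other than progression. Footnote r agrees: "A tumor assessment is to be performed for participants who discontinued the study for reasons other than disease progression".
- Section 8.11.2 gives the SoA its force: "All assessments must be performed as per SoA (Section 1.3".

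The other side:

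- Section 8.1.1 says that, absent clinical deterioration, "any initial assessment of radiological progressive disease should be confirmed by a repeat evaluation" at the next assessment.
- Appendix 8 states: "Response evaluation through use of iRECIST requires collection of tumor assessment data after radiographic progression per RECIST v1.1". It then has target, non-target and new lesions followed at each assessment after RECIST v1.1 progression.
- Section 4.1 says "treatment beyond progressive disease (i.e. due to pseudo-progression) according to RECIST Version 1.1 can be considered after initial dose", with Sponsor and Investigator agreement. Section 7.1 gives the criteria.

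iRECIST is used in three places: an exploratory objective in Section 3 (Table 3), the efficacy methods in Table 13, and a sensitivity analysis in Section 9.4.2 that is optional.

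**The concern.** iRECIST adds to RECIST 1.1 by looking at what happens after a first apparent progression: whether it is confirmed, or whether the tumor later shrinks. That needs scans after progression. The table that sites work from stops scheduling scans at that moment, while the text describing response evaluation assumes they continue.

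A site could follow either instruction and believe it was compliant. The resulting gaps in post-progression data would reflect which page a site relied on, not anything about the participants. They could not be repaired later: the Sponsor calculates iRECIST responses by program from lesion measurements recorded in the eCRF, so a scan that was not taken leaves nothing to calculate from.

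**Working it through.** No arithmetic applies: the plan states no figure on this point, and no hypothesis test is planned (Section 9.1). The check sets the instructions side by side.

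| Situation at first RECIST v1.1 progression | SoA footnotes o and r, read literally | Section 8.1.1 | Appendix 8 |
|---|---|---|---|
| Treatment continues, no clinical deterioration | No further interval given | Repeat at the next assessment | Lesions followed at every later assessment |
| Treatment stops, no clinical deterioration | No later scan; the post-treatment scans are for other reasons for stopping | Repeat asked for; no exemption | No exemption |
| Clinical deterioration | No later scan | Repeat not asked for | No exemption |

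The first two rows conflict directly with Section 8.1.1. All three differ from Appendix 8.

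**Step 1: does Section 8.1.1 or Appendix 8 supply its own scan date?** No. Section 8.1.1 takes its imaging from the SoA and places the repeat at the next assessment. Appendix 8 likewise refers to assessment time points after progression. Both depend on a calendar that footnote o does not extend past progression, and Section 8.11.2 makes that calendar binding.

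**Step 2: what follows for iRECIST response?** Appendix 8 describes iRECIST as an extension of RECIST v1.1 that permits response assessment after progression, with RECIST v1.1 conventions applying unless it says otherwise. The two sets of criteria can therefore part only through post-progression data.

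- Footnote o followed literally: no scheduled scan after progression during treatment, so iRECIST ORR and DCR equal the RECIST 1.1 values for those participants.
- Section 8.1.1 followed: participants without clinical deterioration have at least one later assessment, and the two can differ.
- Sites divided between the two: iRECIST summaries mix participants who could show a later response with participants who could not.

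**Step 3: does the same hold for PFS?** This cannot be shown. How iRECIST dates and counts an unconfirmed progression is not set out in the readable text, and Appendix 8 refers to the publication for the full criteria.

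**Step 4: which endpoints are touched?** The primary endpoints are adverse events and DLTs. Secondary ORR, DCR, DoR and PFS use RECIST 1.1, for which scanning to progression is enough. Only the iRECIST analyses depend on the later scans.

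**The case against.** The strongest reply is that the plan already asks for these scans. Section 8.1.1 wants first progression confirmed, Appendix 8 repeats the instruction lesion type by lesion type, and Section 8.1.1 lets the Investigator repeat CT at any time when progression is suspected. Footnote o says progression without specifying first RECIST progression, and its next sentence ties progression to stopping treatment. Section 7.1 lists progression as a reason to stop only where there is consensus that the participant will not benefit. A site could therefore read the footnote as running until the progression that ends treatment, and take the next 8- or 12-week date as the confirming time point. A participant treated beyond progression who later stops for another reason might also qualify for the end-of-treatment and safety follow-up scans.

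Much of this stands. It shows that the literal reading is an inference, though a reasonable one given that the footnote opens with RECIST 1.1 and Section 8.11.2 defers to the SoA. It also rules out a stronger conclusion that a reader might draw: that iRECIST results will reproduce RECIST 1.1 throughout the trial and that no first progression will ever be confirmed. That would require every site to apply footnote o literally and disregard Section 8.1.1 and Appendix 8, which the documents do not support.

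The reply does not remove the contradiction. It shows that two compliant sites can act differently.

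**Conclusion.** The point holds as an internal contradiction over imaging after progression. The exploratory iRECIST data would be incomplete according to site practice. For participants at sites that apply footnote o literally, iRECIST ORR and DCR could not differ from RECIST 1.1, apart from the narrow late-discontinuation case noted above or scans taken at the Investigator's discretion.

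The size cannot be given as a number: the documents state neither how many participants are expected to continue beyond progression nor how sites will read the footnote. The conclusion assumes that progression in footnote o means RECIST v1.1 progression. Identity of iRECIST and RECIST 1.1 PFS might also be inferred, but the readable text does not establish it.

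The consequence is modest. The primary endpoints and the RECIST 1.1 secondary endpoints are not affected, and the iRECIST sensitivity analysis is optional. The correction is still worth making because it is cheap and missed scans cannot be recovered.

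**What to change.** Reconcile footnotes o and r with Section 8.1.1 and Appendix 8:

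- Amend footnote o so that, for participants who continue treatment beyond RECIST v1.1 progression, tumor assessments continue at the same interval until treatment discontinuation, including the confirming assessment in Section 8.1.1.
- State whether that repeat assessment also applies to participants who stop treatment at first progression without clinical deterioration. Section 8.1.1 does not exempt them, so an amendment limited to continued treatment would leave that conflict in place. Align footnote r with the answer.
- Correct a related cross-reference: Section 8.1.1 points to Section 6.7 for continuing treatment, but Section 6.7 concerns access after the study and the criteria are in Section 7.1.

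The cost is SoA wording and continued imaging for participants treated beyond progression, which Section 8.1.1 and Appendix 8 already call for. If the repeat assessment is confirmed for participants who stop at first progression, they would also need that scan.
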